2.2 Exclusion Criteria

2.2.1 Patient has not recovered from acute toxic effects of all prior therapies.

2.2.2 Patients who are receiving any other investigational agents.

2.2.3 History of allergic reactions attributed to compounds of similar chemical or biologic composition to vorinostat or lenalidomide.

- 2.2.4 Uncontrolled intercurrent illness including, but not limited to, ongoing or active infection, dyspnea at rest, symptomatic congestive heart failure, history of thromboembolism unrelated to central line, patients with known predisposition syndrome for thromboembolism, patients receiving anticoagulation therapy, unstable angina pectoris, cardiac arrhythmia, patients receiving enzyme inducing anticonvulsants, patients receiving valproic acid, patients receiving antiplatelet agents (aspirin, anti-inflammatory drugs), or psychiatric illness/social situations that would limit compliance with study requirements.
- 2.2.5 Pregnant women are excluded from this study due to the potential for teratogenic effects. Because there is an unknown but potential risk for adverse events in nursing infants secondary to treatment of the mother with these agents, breastfeeding should be discontinued if the mother is being treated and not resumed until 28 days after completing therapy.
- 2.2.6 HIV-positive patients on combination antiretroviral therapy are ineligible because of the potential for pharmacokinetic interactions with these agents. In addition, these patients are at increased risk of lethal infections when treated with marrow-suppressive therapy.

2.4 Inclusion of Women and Minorities

Both males and females of all races and ethnic groups are eligible for this trial.

3. TREATMENT PLAN

Treatment will be administered primarily on an outpatient basis, although may be given inpatient based on location or status of patient. Reported adverse events and potential risks are described in Section 7. Appropriate dose modifications are described in Section 6. No investigational or commercial agents or therapies other than those described below may be administered with the intent to treat the patient's malignancy.

Each cycle will begin with ANC >1000 and platelet count >100 without transfusion support. At the beginning of each cycle pregnancy testing must be confirmed negative for females of child bearing potential and counseling regarding pregnancy risks must be confirmed for all patients

4. STUDY SCHEMA

This is a phase I study of the combination of vorinostat and lenalidomide.

Cycle		Days			
Medication	Route	1-7	8-14	15-21	22-28

Lenalidomide	PO/GT/J T	X	X	X	Rest
Vorinostat	PO/GT/J T	X	Rest	X	Rest

Dose Escalation Schedule		
Dose Level	Dose	
	Lenalidomide mg/m²	Vorinostat mg/m²
Level 1	25	180
Level 2	50	180
Level 3	100	180
Level 4	150	180
Level 5	150	230

5. ADVERSE EVENT REPORTING

All Adverse Events of any grade must be reported in routine study data submissions. AEs reported to the IRB in an expedited manner (i.e. adverse events meeting the IRB's definition of an unanticipated problem) must also be reported in routine study data submissions. All relevant follow-up information concerning adverse events should be collected as soon as possible.

6. STUDY CALENDAR

Baseline evaluations are to be conducted within 2 weeks prior to start of protocol therapy. Scans and x-rays must be done ≤ 4 weeks prior to the start of therapy. In the event that the patient's condition is deteriorating, laboratory evaluations should be repeated within 48 hours prior to initiation of the next cycle of therapy.

Timing of protocol therapy administration and response assessment studies are based on schedules derived from the experimental design or on established standards of care. Minor unavoidable departures (up to 72 hours) from protocol directed therapy and/or disease evaluations for valid clinical, patient and family logistical, or facility, procedure and/or anesthesia scheduling issues are acceptable (except where explicitly prohibited within the protocol).

Procedure	Pre-Study	Wk 1	Wk 2	Wk 3	Wk 4	Wk 5	Wk 6	Wk 7	Wk 8	Wk 9	Wk 10	Wk 11	Wk 12 ^c	Off Study ^d
Informed consent	X													
Lenalidomide		A	A	A		A	A	A		A	A	A		
Vorinostat		B		B		B		B		B		B		
Demographics	X													
Medical history	X													
Concurrent meds	X	X-----X												
Physical exam	X	X		X		X		X		X		X		X
Vital signs	X	X		X		X		X		X		X		X
Height	X	X		X		X		X		X		X		X
Weight	X	X		X		X		X		X		X		X
Performance status	X	X		X		X		X		X		X		X
CBC w/diff, plts	X	X		X		X		X		X		X		X
Serum chemistry ^a	X	X		X		X		X		X		X		X
ECG	X												X	x
MRI brain/spine ^e	X												X	
Adverse event		X-----X											X	

evaluation														
B-HCG	X ^b	X ^b	X ^b	X ^b	X ^b				X ^b				X ^b	

A: Dose as assigned; administration schedule
 
B: Dose as assigned; administration schedule
 
a: Albumin, alkaline phosphatase, total bilirubin, bicarbonate, BUN, calcium, chloride, creatinine, glucose, LDH, phosphorus, potassium, total protein, SGOT [AST], SGPT [ALT], sodium.
 
b: Serum or urine pregnancy test (women of childbearing potential). Obtain 10-14 days prior to study enrollment and again within 24 hours prior to Day 1 of each cycle. Obtain weekly during cycle 1. Females with irregular menstruation must have a pregnancy test every 14 days while receiving protocol therapy (including breaks in treatment). Pregnancy test is also required if patient misses her period or has unusual menstrual bleeding. Pregnancy testing must also occur at Day 28 (and at Day 14 if female has irregular menstruation) after lenalidomide discontinuation).
 
c: Continue pattern of measurements while on study.
 
d: Off-study evaluation
 
e: As indicated based on diagnosis and tumor location.

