1. OBJECTIVES

1.1 Primary Objectives

- 1.1.1** To conduct a phase I study to evaluate the safety and tolerability of this combination of chemotherapy agents.
- 1.1.2** To determine the response of children with recurrent or refractory central nervous system tumors with this combination of chemotherapy agents.

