1.1 Study Design/Endpoints

This is a single arm phase I dose escalation study, designed to determine the safety of lenalidomide and vorinostat when administered to children with relapsed or progressive central nervous system tumors. The starting dose and schedule are indicated in the treatment plan section. The study will follow a standard 3+3 patient cohort escalation design with escalation through five dose levels. Thus, a minimum of 6 patients and a maximum of 20 patients will be required to establish a recommended phase II dose. At Johns Hopkins All Children's Hospital, approximately 50-60 patients with brain and spinal cord tumors come for evaluation and treatments. Many of these patients relapse or have progressive disease. We anticipate the enrollment of approximately 20 patients during the study period at an enrollment rate of approximately 10 subjects per year. With this sample size, the 80% confidence interval if two, four, six, eight and ten patients show responses will be (1.8%-16.8%), (5.9%-24.9%), (10.9%-32.5%), (16.2%-39.7%) and (21.8%-46.6%) respectively.

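### Between baseline and off study, ECGs are scheduled only in Wk 12 and its repeats, nominally a rest week for both drugs; none falls in a dosing week or in cycles 1-2

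*Protocol*

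**What the plan says.** The Section 4 schema of the protocol gives a 28-day cycle in four blocks of seven days. Its two rows are "Lenalidomide PO/GT/J T X X X Rest" and "Vorinostat PO/GT/J T X Rest X Rest". Lenalidomide is therefore taken on days 1-21 and vorinostat on days 1-7 and 15-21. Days 22-28 are a rest for both.

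The Section 6 calendar lays this out over 12 weeks. Its drug rows are "Lenalidomide A A A A A A A A A" and "Vorinostat B B B B B B", and both are blank in Wk 4, 8 and 12. The ECG row has three marks: Pre-Study, Wk 12 and Off Study. Physical exam, vital signs, CBC and serum chemistry are marked in Wk 1, 3, 5, 7, 9 and 11, as well as at Pre-Study and Off Study.

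The Wk 12 column carries footnote c: "c: Continue pattern of measurements while on study". Footnote d identifies the last column only as the off-study evaluation.

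The first primary objective (Section 1.1) is "To conduct a phase I study to evaluate the safety and tolerability of this combination of chemotherapy agents".

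**The concern.** The trial has chosen to collect ECGs, and safety of the combination is what it first sets out to learn. Yet the one ECG placed between baseline and off study falls in a week when, on the nominal schedule, the patient takes neither drug. The other recurring safety measurements named above are all placed in weeks when both drugs are taken. The Wk 12 ECG shares its column with the MRI, so it may have been placed there to go with the response assessment.

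At stake is what the ECG data can show. A tracing taken after some drug-free days can reveal a change that persists. It cannot be relied on to reveal one that is present only during dosing. On-drug tracings that were never taken cannot be recovered at analysis. The first post-baseline ECG is also late for this population: Section 2.1.6 requires a life expectancy of only more than 8 weeks. A patient who stops before Wk 12 has no scheduled ECG between baseline and the Off Study evaluation.

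**Working it through.** The plan states no sample size, power or error rate that bears on this point. The check is a reading of two tables against each other, plus day arithmetic.

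**1. Do schema and calendar agree on the dosing weeks?** Week w is week ((w - 1) mod 4) + 1 of its cycle. Lenalidomide is given in cycle weeks 1, 2 and 3; vorinostat in cycle weeks 1 and 3.

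| | From the Section 4 schema | Marked in the Section 6 calendar |
|---|---|---|
| Lenalidomide | Wk 1-3, 5-7, 9-11 | Wk 1-3, 5-7, 9-11 |
| Vorinostat | Wk 1, 3, 5, 7, 9, 11 | Wk 1, 3, 5, 7, 9, 11 |
| Neither drug | Wk 4, 8, 12 | Wk 4, 8, 12 |

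The two tables agree. Of the 12 weeks, 9 have at least one drug, 6 have both and 3 have neither.

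**2. Where does the Wk 12 ECG fall?** Wk 12 covers study days 11 × 7 + 1 = 78 to 12 × 7 = 84. Cycle 3 starts on day 2 × 28 + 1 = 57, so these are cycle days 22-28. The last scheduled dose of either drug in cycle 3 is on day 56 + 21 = 77. The ECG therefore comes 78 - 77 = 1 to 84 - 77 = 7 days after it.

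**3. Do the repeats change this?** Twelve weeks is exactly three 28-day cycles, so every repeat lands in the same week of a cycle.

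| ECG week | Study days | Cycle | Week of cycle |
|---|---|---|---|
| 12 | 78-84 | 3 | 4 (rest) |
| 24 | 162-168 | 6 | 4 (rest) |
| 36 | 246-252 | 9 | 4 (rest) |
| 48 | 330-336 | 12 | 4 (rest) |

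**4. Count, between baseline and off study.** ECGs scheduled in a dosing week: 0. ECGs scheduled in cycle 1 (Wk 1-4): 0. In cycle 2 (Wk 5-8): 0. The earliest is day 78, which is 78 - 28 = 50 days after cycle 1 ends and 78 - 56 = 22 days after cycle 2 ends.

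**5. Could the plan's own flexibility move it onto dosing days?**

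- *Timing allowance.* Section 6 accepts "Minor unavoidable departures (up to 72 hours) from protocol directed therapy and/or disease evaluations". Three days earlier than day 78 is day 75, a dosing day; three days later than day 84 is day 87, which is day 3 of cycle 4. But this is a tolerance for departures, and it names therapy and disease evaluations, not ECGs.
- *Delayed cycles.* Section 3 starts each cycle only once counts allow. If one week is lost before cycle 2 or 3, cycle 3 starts on day 64, and days 78-84 become cycle days 78 - 64 + 1 = 15 to 84 - 64 + 1 = 21, when both drugs are given. This holds only if the calendar columns stay tied to study weeks and do not shift with the cycle, and the documents do not say which.

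Either route could produce an on-drug ECG in some patients. Neither schedules one.

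**The case against.** The strongest reply is that nothing here is contradictory. Calendar and schema agree, and an ECG after three cycles is a reasonable check for persistent or cumulative change. The supplied text does not say that either drug affects rhythm or conduction, or that any effect would be brief; Section 3 refers to potential risks in a Section 7 that is not in the supplied text. Patients are not unmonitored on drug: exam, vital signs and chemistry (including potassium and calcium) fall in both-drug weeks, and adverse events of every grade are reported. All of this stands. It lowers the importance of the point but leaves the reading of the table intact: symptoms and chemistry do not replace a tracing, and the plan gives no reason for taking it off drug.

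A reader might go further in four ways that the documents do not support.

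- *That no ECG falls in the cycle where escalation is decided.* The SAP (Section 1.1) says "The study will follow a standard 3+3 patient cohort escalation design with escalation through five dose levels" but the supplied text gives no DLT or escalation window. The SAP sends the reader to a section 5 for the DLT definition, and Section 5 of the protocol as supplied covers adverse event reporting only. Pages were removed before review, so the absence is not counted as an error. A first-cycle window is an assumption. If the window were one or two cycles it would contain no scheduled ECG; if it were 12 weeks, only the Wk 12 one.
- *That the Off Study ECG is necessarily off drug.* Its interval from the last dose is not stated.
- *That no patient will ever have an ECG on drug.* Delayed cycles or the timing allowance could produce one.
- *That a drug effect on the ECG would be missed and a clean cardiac result reported.* The duration of any effect is not in the documents, and the SAP announces no ECG analysis.

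**Conclusion.** The point holds as a scheduling gap. On the nominal schedule, the calendar places no ECG between baseline and off study in a week when either drug is given (0 of 9 dosing weeks in each 12) and none in cycles 1-2. The planned on-study ECG comes 1 to 7 days after the last scheduled dose of either drug, at Wk 12 and at each repeat.

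This rests on cycles running without delay and on sites following the calendar as printed. What it costs in lost safety information cannot be sized from the documents. If an ECG effect outlasts the drug by more than a week, Wk 12 could still show it; if it fades sooner, Wk 12 may show it in part or not at all. Both are assumptions. The point deserves correction because the trial's first aim is safety, the remedy is cheap, and data not collected on drug cannot be recovered later.

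**What to change.** Reconcile the ECG row with the drug rows in the Section 6 table. Move the Wk 12 ECG, and its repeats under footnote c, to an existing visit in a week when both drugs are taken. The week, and the timing within the day, are for the sponsor to choose. Wk 11 is the nearest such visit; an earlier one would also give data in the first cycles. Because the pattern repeats every three cycles, an ECG in a both-drug week stays in one (Wk 11 leads to Wk 23 and 35, each the third week of a cycle). Keep the Pre-Study and Off Study ECGs.

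In the same edit, state when the Off Study ECG falls relative to the last dose, and whether the calendar columns shift when a cycle is delayed. If a drug-free ECG is intended, the protocol should say so and why.

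The cost is a calendar amendment. Exam, vital signs and chemistry are already done at the candidate visits, so no visit and no ECG is added, and no dose or treatment rule changes. The downside is that the ECG no longer coincides with the Wk 12 MRI. Having both an early and a later on-drug ECG in the first 12 weeks would add one ECG per patient.

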1.1 Study Design/Endpoints

This is a single arm phase I dose escalation study, designed to determine the safety of lenalidomide and vorinostat when administered to children with relapsed or progressive central nervous system tumors. The starting dose and schedule are indicated in the treatment plan section. The study will follow a standard 3+3 patient cohort escalation design with escalation through five dose levels. Thus, a minimum of 6 patients and a maximum of 20 patients will be required to establish a recommended phase II dose. At Johns Hopkins All Children's Hospital, approximately 50-60 patients with brain and spinal cord tumors come for evaluation and treatments. Many of these patients relapse or have progressive disease. We anticipate the enrollment of approximately 20 patients during the study period at an enrollment rate of approximately 10 subjects per year. With this sample size, the 80% confidence interval if two, four, six, eight and ten patients show responses will be (1.8%-16.8%), (5.9%-24.9%), (10.9%-32.5%), (16.2%-39.7%) and (21.8%-46.6%) respectively.

Statistical analysis will be conducted at the completion of the study after accrual goals have been met. We will describe the baseline demographic and clinical characteristics, adverse events and response in all patients. Continuous variables will be summarized using mean, standard deviations, median, maximum and minimum values. Discrete variables will be summarized using counts and percentages with the corresponding 95% confidence intervals where appropriate. Time to event variables will be analyzed using Kaplan Meier methods. Progression free survival (PFS) and overall survival rates and the corresponding confidence intervals at fixed time points will be derived from the Kaplan Meier estimate. PFS will be defined as the time between date of first dose of the study therapy and date of progression or death, whichever occurs first. Patients will be censored on the date of last tumor assessment if they remain alive and do not have tumor progression. Surviving patients who did not receive any on-treatment tumor assessment will be censored on the date of first dose of study medication. A window of 1 week prior to the PFS rate time points will be applied to account for different tumor assessments dates, since not all patients adhere to scheduled dates. Descriptive statistics will be used to summarize time to event endpoints, if Kaplan Meier methods fail to provide estimates. All statistical analysis will be performed using SAS software version v 9.3 (SAS Institute, Inc., Cary, NC)

All toxicities will be graded on all patients that receive any amount of study drug. Only patients who receive 12 week of therapy will be used for final analysis. The dose escalation schema, definition of DLT, and endpoints are in section 5.

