1.2 Sample Size/Accrual Rate

We anticipate the enrollment of approximately 20 patients during the study period at an enrollment rate of approximately 10 subjects per year.

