1.3 Stratification Factors

The MTD determination and dose escalation are uniform per stratum.

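### The stated maximum of 20 patients does not follow from a standard 3+3 over five dose levels; the maximum is 30, and the SAP's own 80% intervals are computed at 30

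*SAP*

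**What the plan says.** SAP 1.1 describes a "standard 3+3 patient cohort escalation design with escalation through five dose levels". Protocol section 4 lists the same five levels, 1 to 5, under "Dose Escalation Schedule". The SAP then draws its sample size from the design: "Thus, a minimum of 6 patients and a maximum of 20 patients will be required to establish a recommended phase II dose".

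The paragraph goes on to anticipate about 20 patients at about 10 per year, and SAP 1.2 repeats this: "We anticipate the enrollment of approximately 20 patients during the study period". Precision for response follows directly, introduced by the words "With this sample size, the 80% confidence interval if two, four, six, eight and ten patients show responses will be". The limits printed there are 1.8–16.8% for 2 responders, 5.9–24.9% for 4, 10.9–32.5% for 6, 16.2–39.7% for 8 and 21.8–46.6% for 10.

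Two further statements bear on the count. SAP 1.1 says of the operating rules: "The dose escalation schema, definition of DLT, and endpoints are in section 5". SAP 1.3 says: "The MTD determination and dose escalation are uniform per stratum". It does not define the strata.

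**The concern.** The SAP presents 20 as the consequence of the design, but a 3+3 through five levels can call for more. Two outcomes are then possible. If 20 is not enforced, the trial can pass its own stated maximum. If it is enforced, the trial can stop before it has the recommended phase II dose that the sentence promises. The text available for review does not say which applies.

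The intervals raise a second problem. Response is a primary objective in Protocol 1.1.2, and these intervals are the only precision statement for it. If they rest on a different N from the one stated just before them, they misdescribe what the planned trial can show.

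**Working it through.** **Inputs.** Standard 3+3, five levels, minimum 6, maximum 20, about 10 patients per year, and five 80% intervals for 2, 4, 6, 8 and 10 responders (SAP 1.1 and 1.2; levels confirmed in Protocol section 4). The usual 3+3 rules are assumed: 3 patients per level; escalate on 0/3 dose-limiting toxicities (DLTs); expand to 6 on 1/3; escalate on 1/6; stop escalating on 2 or more. One stratum is assumed.

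**Step 1: the stated minimum.** With 0/3 at level 1 and at least 2/3 at level 2, a dose is declared after 3 + 3 = 6 patients. This reproduces the SAP's 6, provided six patients are not required at the recommended dose. If they are, level 1 needs three more and the minimum is 6 + 3 = 9.

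**Step 2: the stated maximum.** No level takes more than 6, so the maximum is 5 × 6 = 30. Enumerating every path gives totals of 3, 6, 9, …, 27, 30 under both conventions. The figure of 20 is not reproduced. It is not a multiple of 3, so it is not an attainable count of evaluable patients.

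**Step 3: the N behind the intervals.** The exact (Clopper-Pearson) 80% limits for x responders in n are:

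- lower = the 0.10 quantile of Beta(x, n − x + 1)
- upper = the 0.90 quantile of Beta(x + 1, n − x)

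| Responders | Printed in SAP 1.1 | Exact, n = 30 | Exact, n = 20 |
|---|---|---|---|
| 2 | 1.8–16.8% | 1.8–16.8% | 2.7–24.5% |
| 4 | 5.9–24.9% | 5.9–24.9% | 9.0–36.1% |
| 6 | 10.9–32.5% | 10.9–32.5% | 16.6–46.7% |
| 8 | 16.2–39.7% | 16.2–39.7% | 24.9–56.7% |
| 10 | 21.8–46.6% | 21.8–46.6% | 33.8–66.2% |

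All ten limits match n = 30. A search over n = 12 to 60, four confidence levels and five interval methods found no other fit; the next best was off by 1.3 percentage points. At n = 20 two printed intervals exclude their own estimate: 8/20 = 40% lies above 39.7%, and 10/20 = 50% lies above 46.6%.

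**Step 4: how often 20 would be exceeded.** The documents give no DLT rates, so the four profiles below are assumptions. Path probabilities were enumerated exactly and sum to 1.

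| Assumed DLT rates, levels 1–5 | Expected N | P(N > 20) | of which exactly 21 | of which 24 or more |
|---|---|---|---|---|
| *Six not required at the recommended dose (minimum 6)* | | | | |
| 5% at every level | 16.2 | 10.5% | 9.2% | 1.4% |
| 10% at every level | 15.5 | 18.9% | 14.7% | 4.2% |
| 5, 10, 15, 20, 25% | 15.7 | 20.1% | 15.0% | 5.1% |
| 10, 20, 30, 40, 50% | 12.0 | 6.4% | 4.8% | 1.6% |
| *Sensitivity: six required (minimum 9)* | | | | |
| 5% at every level | 18.7 | 37.5% | 30.4% | 7.1% |
| 10% at every level | 17.7 | 43.3% | 29.7% | 13.6% |
| 5, 10, 15, 20, 25% | 18.0 | 41.0% | 26.6% | 14.5% |
| 10, 20, 30, 40, 50% | 14.2 | 14.4% | 9.3% | 5.1% |

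Components may differ from their total by 0.1 through rounding. Reaching exactly 30 is rare: below 0.04% in the first block and at most about 0.16% in the second.

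**Step 5: accrual.** 20 ÷ 10 = 2 years; 30 ÷ 10 = 3 years.

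**The case against.** The best case for the plan is that little would go wrong in practice. Under the convention that fits the stated minimum, the expected number is 12.0 to 16.2, most overruns are a single patient, and an anticipated enrolment of approximately 20 could be read to cover 21. The larger overrun probabilities require six patients at the recommended dose, which contradicts the stated minimum of 6. This stands: those figures are a sensitivity case only, and a large shortfall is unlikely.

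The escalation rules may also contain a cap. SAP 1.1 places them in a section 5, and section 5 of the protocol text available covers adverse event reporting, so the rules could not be read. This limits what can be said about the consequence of reaching 20. It does not rescue the sentence, which derives 20 from a standard 3+3, and a cap stated elsewhere would not make intervals computed at n = 30 right for n = 20. Separate escalation by stratum, or replacement of inevaluable patients, would only raise the total.

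Finally, the 80% intervals are planning illustrations. No decision threshold in the available text uses them, and SAP 1.1, 1.4 and 1.5.2 refer to 95% intervals for reporting. That also stands: final inference would not change. The planning statement of precision is still wrong.

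**Conclusion.** The concern holds. A standard 3+3 through five levels has a maximum of 30 evaluable patients, 10 more (50%) than the SAP states. This rests on the usual limit of six per level and on one stratum; it does not depend on whether six are required at the recommended dose.

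The mismatch in the intervals needs no assumption about escalation rules, DLT rates or strata. They were computed at n = 30 and are attached to a sample size of about 20. For 2 responders, the upper limit is printed as 16.8% when 20 patients would give 24.5%.

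The practical risk is moderate. On the assumed profiles, more than 20 patients would be needed in 6.4–20.1% of trials under the convention that fits the stated minimum, and 24 or more in 1.4–5.1%. The error is a wrong bound and two different sample sizes in one paragraph, and it should be corrected before the plan is relied on.

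**What to change.** State which 3+3 convention applies, then take one of two routes.

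1. **Give the true bound.** For example: *a minimum of 6 patients (9 if six are required at the recommended dose) and a maximum of 30 evaluable patients (5 levels × 6), plus any replacements; approximately 20 is the anticipated number.* Give accrual as up to about 3 years at 10 per year, in SAP 1.1 and 1.2. The printed intervals can stay if they are labelled as n = 30; add the n = 20 intervals if 20 remains the anticipated enrolment.
2. **Keep 20 as an explicit cap.** Remove the claim that 20 is the most that could be required, state that the trial may end without a recommended phase II dose, and replace the five intervals with the n = 20 values tabulated above.

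Under either route, say whether the strata mentioned in SAP 1.3 escalate separately, since that would change the maximum.

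The drafting cost is small: a sentence or two, the accrual estimate and at most five intervals. Route 1 adds no patients beyond those the stated design can already call for, but it raises the declared ceiling by half and lengthens possible accrual by a year at the stated rate, so feasibility and approvals would need to be checked. Route 2 avoids that, at the price of admitting that the dose-finding aim may not be met.

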1.4 Analysis of Secondary Endpoints

Responses will be reported as a secondary endpoint. Every report should contain all patients included in the study. For the response calculation, the report should contain at least a section with all eligible patients. Another section of the report may detail the response rate for evaluable patients only. However, a response rate analysis based on a subset of patients must explain which patients were excluded and for which reasons. It is preferred that 95% confidence limits are given.

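### The five 80% confidence intervals for response are exact limits for 30 patients, but the stated sample size is about 20 (maximum 20)

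*SAP*

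**What the plan says.** SAP 1.1 (Study Design/Endpoints) describes a "standard 3+3 patient cohort escalation design with escalation through five dose levels" and says that "a minimum of 6 patients and a maximum of 20 patients will be required" to reach a recommended phase II dose. It then expects about 20 patients, accrued at about 10 per year. SAP 1.2 repeats the figure: "We anticipate the enrollment of approximately 20 patients".

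Directly after the accrual statement, SAP 1.1 gives the expected precision for response: "With this sample size, the 80% confidence interval if two, four, six, eight and ten patients show responses will be (1.8%-16.8%), (5.9%-24.9". The third interval is 10.9–32.5%, and the list ends with "16.2%-39.7%) and (21.8%-46.6%) respectively".

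Protocol 1.1.2 lists response as a primary objective. SAP 1.4 treats it differently: "Responses will be reported as a secondary endpoint".

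**The concern.** The sentence ties its intervals to the sample size just given, which is about 20. Two of them fail a check that needs no software. Eight responders out of 20 is 40%, but the printed interval stops at 39.7%. Ten out of 20 is 50%, but the printed interval stops at 46.6%. An ordinary binomial interval contains its own observed proportion, so these intervals must have been computed with a larger denominator.

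No other precision figures are given for response. Protocol 1.2.1 plans a comparison of response with historical controls, and 1.2.3 plans to use the efficacy data to recommend larger studies. A reader judging what this trial can contribute to either aim would expect narrower and lower intervals than 20 patients can give.

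**Working it through.** **Inputs (all from SAP 1.1; n also from SAP 1.2)**
- n: about 20, maximum 20.
- Confidence level: 80% with two limits, so α = 0.20, or 10% in each tail.
- Responders: x = 2, 4, 6, 8, 10.
- The five printed intervals.

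**Formula.** The exact (Clopper-Pearson) limits are
- lower = the α/2 quantile of Beta(x, n − x + 1)
- upper = the 1 − α/2 quantile of Beta(x + 1, n − x)

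For x = 8 and n = 20, the lower limit is the 0.10 quantile of Beta(8, 13) = 24.91%, and the upper limit is the 0.90 quantile of Beta(9, 12) = 56.73%.

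**Step 1: reproduce the plan's figures.** The formula was evaluated over a range of n and compared with the ten printed limits:

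| n | Sum of absolute gaps (points) | Largest gap (points) |
|---|---|---|
| 18 | 132.2 | 25.5 |
| 20 | 100.1 | 19.6 |
| 24 | 50.8 | 10.1 |
| 29 | 7.07 | 1.46 |
| **30** | **0.24** | **0.044** |
| 31 | 6.66 | 1.32 |

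At n = 30 the gaps are rounding only. The neighbouring values of n are already off by more than a point.

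**Step 2: could another method at n = 20 explain the figures?** Wald, Wilson, Agresti-Coull, Jeffreys and exact limits were tried at several confidence levels, as were exact limits that are each one-sided 80%. The closest variant at n = 20 still misses by 16.6 points on its worst limit.

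**Step 3: correct values at n = 20.** Widths and ratios were computed before rounding the limits.

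| Responders | Observed rate at n = 20 | Printed 80% interval | Exact 80%, n = 30 | Exact 80%, n = 20 | Width: printed → n = 20 | Ratio |
|---|---|---|---|---|---|---|
| 2 | 10% | 1.8–16.8 | 1.79–16.78 | 2.7–24.5 | 15.0 → 21.8 | 1.45 |
| 4 | 20% | 5.9–24.9 | 5.94–24.90 | 9.0–36.1 | 19.0 → 27.0 | 1.42 |
| 6 | 30% | 10.9–32.5 | 10.86–32.47 | 16.6–46.7 | 21.6 → 30.1 | 1.40 |
| 8 | 40% | 16.2–39.7 | 16.20–39.68 | 24.9–56.7 | 23.5 → 31.8 | 1.35 |
| 10 | 50% | 21.8–46.6 | 21.84–46.63 | 33.8–66.2 | 24.8 → 32.4 | 1.31 |

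The printed lower limits are too low by 0.9 points (2.69 − 1.8) to 12.0 points (33.82 − 21.8). The printed upper limits are too low by 7.7 points (24.48 − 16.8) to 19.6 points (66.18 − 46.6).

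**Step 4: where might 30 come from?** Five dose levels with six patients each give 5 × 6 = 30, the full expansion of a five-level 3+3. This is an inference; the documents do not say so.

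**The case against.** The strongest argument is that little turns on these figures. They illustrate precision in a small phase I study. They do not set the sample size, which comes from the 3+3 design and accrual. The final report will compute its intervals from the patients actually treated. The analysis text also refers to 95% limits: SAP 1.1 asks for "counts and percentages with the corresponding 95% confidence intervals where appropriate", and SAP 1.4 and 1.5.2 also refer to the 95% level. This stands, and it caps the weight of the point. It does not make the printed figures right.

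A second argument is that 30 may have been the intended size, in which case the intervals are correct and the statements of 20 are wrong. The documents cannot exclude this. They favour 20, which appears twice in SAP 1.1 and again in SAP 1.2. What is established is that n and the intervals are incompatible.

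A third is that the planned size is only approximate. That does not rescue the figures: 30 is half as many again as 20 and exceeds the stated maximum, and even n = 24 leaves a gap of 10.1 points. A smaller denominator makes matters worse. That is possible, because SAP 1.1 limits the final analysis to patients who receive 12 weeks of therapy, whereas SAP 1.4 and 1.5.2 base response on all eligible patients.

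The choice of an 80% level is not an error and is not criticised here.

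**Conclusion.** The concern holds. The printed intervals are exact 80% limits for 30 patients, presented as the precision available from about 20. If 20 is the intended size, all ten limits are too low and all five intervals too narrow; the correct ones are 31% to 45% wider. The n = 20 figures assume the exact method, which is the one that reproduces the printed values, and that all 20 patients are in the denominator. The error should be fixed because response is a primary objective in the protocol and has no other precision statement. It does not affect the safety design, dose escalation or the final analysis.

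**What to change.** Confirm the intended sample size first.

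- **If n = 20:** replace the sentence in SAP 1.1 with: *With 20 patients, the exact (Clopper-Pearson) 80% confidence intervals for 2, 4, 6, 8 and 10 responses are 2.7–24.5%, 9.0–36.1%, 16.6–46.7%, 24.9–56.7% and 33.8–66.2%.* State that all 20 patients are assumed to be in the denominator. This is one sentence; no patients are added, and the only cost is less favourable stated precision.
- **If n = 30:** keep the intervals and reconcile the maximum of 20 and the expected enrolment of about 20 in SAP 1.1, and the repeat in SAP 1.2. At about 10 patients per year, accrual would lengthen from about two years (20 ÷ 10) to about three (30 ÷ 10).

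Optionally, because the analysis text refers to 95% limits, the exact 95% intervals for n = 20 could be shown alongside: 1.2–31.7%, 5.7–43.7%, 11.9–54.3%, 19.1–63.9% and 27.2–72.8%.
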